Pre-specified decrease threshold	A $\geq 50\%$ decrease in sperm concentration, and/or motility, and/or morphology in comparison to Baseline. The mean of values for each of the sperm parameters (measured from 2 separate semen samples) will be used in all analyses. Samples will be collected within a 14-day period, with an ejaculation-free period of ≥ 48 hours and ≤ 7 days.
Reversibility	Reversibility is met when all sperm parameter(s) qualifying the subject to enter into the Monitoring Phase return(s) to greater than 50% of Baseline (ie, to greater than $[0.50 \times \text{mean of 2 sperm collections collected at the Screening visit (eg, Baseline)}]$).
Week 13	The Week 13 Study Visit occurs once a subject completes the first 13 weeks of blinded study drug, and is inclusive of all study assessments performed at the clinic visit and the semen sample collection visits associated with this time point.
Week 26	The Week 26 Study Visit occurs once a subject completes the second 13 weeks of blinded study, and is inclusive of all study assessments performed at the clinic visit and the semen sample collection visits associated with this time point.
OL Week 13	The OL Week 13 Study Visit occurs once a subject completes the first 13 weeks of OL filgotinib, and is inclusive of all study assessments performed at the clinic visit and the semen sample collection visits associated with this time point.

First unblinded interim analysis (IA1)	Unblinded Week 26 analysis to be performed after at least 200 evaluable subjects pooled across studies GS-US-418-4279 (GLPG0634-CL-228) and GLPG0634-CL-227 complete Week 13 and evaluable subjects from Study GS-US-418-4279 complete Week 26 (or OL Week 13) or permanently discontinue from study drug. Referred to as 'Week 26 Analysis' in the SAP.
Second unblinded interim analysis (IA2)	Unblinded Week 26 analysis to be performed after all subjects reach Week 26 and all subjects with a $\geq 50\%$ decrease in sperm concentration, and/or motility, and/or morphology up to Week 26 (or OL Week 13) enter the Monitoring Phase and either meet reversibility criteria or are followed off-treatment for 52 weeks, whichever occurs first. Referred to as 'Week 26 and Reversibility Analysis for Pre-specified Sperm Decreases Up to Week 26' in the SAP.

GLOSSARY OF ABBREVIATIONS AND DEFINITION OF TERMS

5-ASA	5-aminosalicylate
6-MP	6-mercaptopurine
Ab	antibody
AE	adverse event
ALT	alanine aminotransferase
ANCOVA	analysis of covariance

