- 5) Long Term Extension

The study parts are described in the following sections.

Subjects will visit the clinical study center to be evaluated for clinical and laboratory assessments at Screening, Day 1, Week 2, Week 4, Week 8, and Week 13, including semen sample collection during Week 13 visits. Subjects who continue on blinded treatment after the first 13 weeks of treatment will return for Week 20 and Week 26 assessments, including semen sample collection during Week 26 visits.

[figure not shown]
Figure 3-2. Part A (Day 1 through Week 13 Study Visit)

In Part A, all subjects will receive blinded study drug for the first 13 weeks, starting from the Day 1/Randomization Study Visit. At the Week 13 Study Visit, IBD response status (ie, Non-responder vs Responder, see Definition of Terms) will be determined based on the partial Mayo Clinic Score (partial MCS) for subjects with UC, or Crohn’s Disease Activity Index (CDAI) for subjects with CD. In addition, sperm parameters (see Section 6.13 Semen Collection Procedure) will be evaluated to determine whether any of the pre-specified decrease thresholds (see Definition of Terms) have been met.

- Subjects who are Responders whose sperm parameters do not meet a pre-specified decrease threshold will continue blinded study drug in Part B.
- Subjects who are Non-responders whose sperm parameters do not meet a pre-specified decrease threshold will discontinue blinded study drug and commence open-label (OL) filgotinib.
- Subjects whose sperm parameters meet a pre-specified decrease threshold, regardless of IBD response status, will discontinue blinded study drug and enter the Monitoring Phase.

[figure not shown]
Figure 3-3. Part B (After Week 13 through Week 26 Study Visit)

In Part B, all subjects will continue on blinded study drug for up to an additional 13 weeks. Subjects may experience Disease Worsening (see Definition of Terms) of their underlying IBD at any time during blinded study drug treatment (after Week 13 through Week 26). If Disease Worsening is confirmed, sperm parameters will be evaluated to determine whether a pre-specified decrease threshold has been met prior to a study drug change (changing from blinded study drug to OL filgotinib). Based upon the sperm parameters at this time point, subjects may follow one of the following pathways:

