Subjects will visit the clinical study center at Screening, Day 1, Week 2, Week 4, Week 8, and Week 13 (Part A of study). Subjects who are IBD responders at Week 13 without meeting pre-specified sperm decrease thresholds will continue on blinded treatment and return for Week 20 and Week 26 assessments. A pre-specified sperm decrease threshold was defined as a $\geq 50\%$ decrease from baseline in sperm concentration prior to Protocol Amendment 2; and a $\geq 50\%$ decrease from baseline in sperm concentration and/or motility and/or morphology at/after Protocol Amendment 2. Since no subject demonstrated a $\geq 50\%$ decrease in sperm motility or morphology prior to Protocol Amendment 2, this SAP will hereafter refer to a “pre-specified sperm decrease threshold” as a subject demonstrating a $\geq 50\%$ decrease from baseline in sperm concentration and/or motility and/or morphology. Subjects who are non-responders at Week 13 and subjects who have disease worsening after Week 13 up to Week 26 who do not meet pre-specified sperm decrease thresholds will enter the Open-Label Phase and return for visits at Week 2, Week 4, Week 8, and Week 13 during the open-label phase. Subjects who are responders at Week 26/Open-label Week 13 without disease worsening and without meeting pre-specified sperm decrease thresholds may continue taking study drug in the LTE phase for up to 195 weeks (or until they have disease worsening or meet pre-specified sperm decrease threshold[s]).

Subjects who meet pre-specified sperm decrease threshold(s) at any postbaseline visit will stop study drug, switch to a standard of care regimen selected by the investigator (in accordance with the protocol) and enter the Monitoring Phase. Subjects will undergo semen evaluations every 13 weeks starting from their entry into the Monitoring Phase for up to 52 weeks or until reversibility is met, whichever is achieved first. Reversibility is defined as a return to $> 0.5 \times$ (mean of 2 evaluable samples collected at screening visit) of all sperm parameter(s) qualifying the subject for the monitoring phase—based on 2 evaluable samples collected at the monitoring phase visit.

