Week 221	1548	1535	≥ 1548
FU-4*	Last Dose Date any study drug + 30 days	Last Dose Date any study drug + 8 days	Last Dose Date any study drug + 35 days

Note: Primary analysis includes data up to first dose date of open-label filgotinib (if non-missing) or to last dose date of double-blind drug + 7 days (for those who do not switch to open-label filgotinib).

Secondary analysis includes all “on-treatment” data up to the last dose date of any study drug + 7 days.

*FU-4 visit for subjects who have stopped all study drugs and had a 30-day safety FU visit ± 5 days will be displayed in listings only.

Table 3-4. Analysis Visit Windows for On-Treatment Semen Parameters

Analysis Visit	Nominal Day (Study Day)	Lower Limit (Study Day)	Upper Limit (Study Day)
Baseline	1	None	1
Week 13	92	85	112
Week 26	183	170	260
Week 39	274	261	351
Week 52	365	352	442
Week 65	456	443	533
Week 78	547	534	624
Week 91	638	625	715
Week 104	729	716	806
Week 117	820	807	897
Week 130	911	898	988
Week 143	1002	989	1079
Week 156	1093	1080	1170
Week 169	1184	1171	1261
Week 182	1275	1262	1352
Week 195	1366	1353	1443
Week 208	1457	1444	1534
Week 221	1548	1535	≥ 1548

Note: Primary analysis includes data up to first dose date of open-label filgotinib (if non-missing) or to last dose date of double-blind drug + 7 days (for those who do not switch to open-label filgotinib).

Secondary analysis includes all “on-treatment” data up to the last dose date of any study drug + 7 days.

Table 3-5. Analysis Visit Windows for Semen Parameters in Monitoring Phase (Calculated from Last Dose Date of Any Study Drug)

Analysis Visit	Nominal Day (FU Day)	Lower Limit (FU Day)	Upper Limit (FU Day)
MP Week 13	91	8	104
MP Week 26	182	105	195
MP Week 39	273	196	286
MP Week 52	364	287	377

MP = Monitoring Phase; FU = Follow-Up.

NOTE: All visit windows for monitoring phase will be calculated from last dose date of any study drug.

FU Day = visit date – last dose date of any study drug.

Investigator Assessment of ECG Visit Assignment

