A summary of subject disposition will be provided by randomized treatment group and overall. This summary will present the number of subjects screened (rescreens counted once), the number of subjects randomized, and the number of subjects in the safety analysis set. In addition, the number and percentage of subjects in each category below will be summarized:

Double-Blind Study Drug Completion Status Through Week 13

- Completed blinded study drug through Week 13
 - Switched to Monitoring Phase after Week 13 (subject met pre-specified sperm decrease threshold[s])
 - Continued double-blind treatment after Week 13 (responder, subject did not meet pre-specified sperm decrease threshold[s])
 - Switched to Open-Label Filgotinib Phase after Week 13 (non-responder, subject did not meet pre-specified sperm decrease threshold[s])
- Did not complete blinded study drug through Week 13 with reasons for premature discontinuation of study drug

Double-Blind Study Drug Completion Status (> Week 13 Through Week 26)

- Completed blinded study drug through Week 26
 - Switched to Monitoring Phase after Week 26 (subject met pre-specified sperm decrease threshold[s])
 - Continued blinded study drug (responder and no disease worsening, subject did not meet pre-specified sperm decrease threshold[s])
 - Discontinued study drug at Week 26 (non-responder, subject did not meet pre-specified sperm decrease threshold[s])
- Did not complete blinded study drug through Week 26 with reasons for premature discontinuation of study drug

Open-Label Filgotinib Phase Study Drug Completion Status

- Completed open-label study drug through Open-Label Week 13
 - Switched to Monitoring Phase after Open-Label Week 13 (subject met pre-specified sperm decrease threshold[s])
 - Continued open-label filgotinib after Open-Label Week 13 (responder and no disease worsening, subject did not meet pre-specified sperm decrease threshold[s])
 - Discontinued Open-Label Filgotinib Phase at Open-Label Week 13 (non-responder, subject did not meet pre-specified sperm decrease threshold[s])
- Did not complete open-label study drug through Open-Label Week 13 with reasons for premature discontinuation of study drug

LTE Double-Blind Study Drug Completion Status

- Completed LTE Double-Blind Phase of study

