The number and proportion of subjects with a $\geq 50\%$ decrease in sperm concentration at Week 26 (observed cases) will be presented by double-blind treatment group. The number of subjects who have a $\geq 50\%$ decrease in sperm concentration at any time up to Week 26 (to upper bound of analysis visit window) will be displayed to ensure that $\geq 50\%$ decreases from baseline in sperm concentration that fell outside of the analysis visit windows are accounted for.

CONTINUOUS ENDPOINTS	WHILE ON TREATMENT STRATEGY
Population	Semen Analysis Set (subjects with 2 evaluable semen samples collected at baseline and at the Week 13 analysis visit) as defined in Section 3.1.2 of this SAP.
Patient Level Outcome to be Measured	Change and Percentage Change from Baseline (continuous outcome) at Week 13. Outcome is determined based on the mean of 2 evaluable semen samples at a visit, and analysis visit windows are assigned based on first of 2 evaluable semen samples.
Measure of intervention effect and handling of intercurrent events	Measure of treatment effect assuming that the treatment effect prior to the intercurrent event of treatment early termination is of interest. Data included to last dose date double-blind drug + 7 days will be considered “while on-treatment” for those who permanently discontinue double-blind study drug.
Population level summary measure	Median Difference between treatment groups, comparing those assigned to filgotinib versus those assigned to placebo in the change and percentage change from baseline at Week 13 for a continuous outcome.
Estimators	
Main estimator: Quantile regression models will be used to estimate the median difference (filgotinib – placebo) in change and percentage change from baseline at Week 13, 95% CI for the sperm/semen parameter of interest. The CI=RANK option will be specified in PROC QUANTREG in SAS.
 
For sperm concentration (M/mL), the model will include: baseline sperm concentration (continuous).
 
For sperm total motility (%), percent normal morphology, total sperm count (M/ejaculate) and ejaculation volume (mL), the model will include: baseline value for parameter (continuous), and sperm concentration (15 – 50 M/mL, > 50 M/mL).

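### The Week 26 observed-case proportion by blinded arm covers only IBD responders who passed Week 13 with no sperm decrease, and the any-time display that would complete it has no stated by-arm denominator, difference or CI

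*SAP*

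**What the plan says.** **Who leaves blinded drug at Week 13.** Protocol section 3 (Part A) states that men who meet a sperm threshold, "regardless of IBD response status, will discontinue blinded study drug and enter the Monitoring Phase". The protocol's Definition of Terms sets the threshold as at least a 50% "decrease in sperm concentration, and/or motility, and/or morphology in comparison to Baseline", so a fall in motility or morphology alone is enough. IBD non-responders with no decrease move to open-label filgotinib. SAP 1.2 gives the remainder: "Subjects who are IBD responders at Week 13 without meeting pre-specified sperm decrease thresholds will continue on blinded treatment".

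**Which data count by arm.** The note to SAP Table 3-4 reads: "Primary analysis includes data up to first dose date of open-label filgotinib (if non-missing) or to last dose date" of double-blind drug plus 7 days. The Week 13 semen window is Days 85 to 112 and the Week 26 window is Days 170 to 260.

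**What is shown for Week 26.** SAP 6.2 says that the number and proportion with at least a 50% "decrease in sperm concentration at Week 26 (observed cases) will be presented by double-blind treatment group". It adds that the number with such a decrease "at any time up to Week 26 (to upper bound of analysis visit window) will be displayed", so that decreases outside the windows are not missed. The Mantel-Haenszel difference and CI (SAP 6.2 and Appendix 2) are specified for Week 13. Protocol 8.5.2 plans the Week 26 binary endpoint as descriptive only.

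**The concern.** The event being measured removes men from the later denominator. A man whose concentration halves by Week 13 cannot appear in the Week 26 observed-case figure. Men also leave for IBD non-response, which may differ between arms. The figure estimates the rate of new decreases among men who got through Week 13, and SAP 6.2 does not label it so.

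Protocol 1.3.1 chose Week 26 to look at the effect after two spermatogenesis cycles, and Protocol 8.11 plans publication of the second interim analysis. If harm came early, the published Week 26 arms would look alike by construction. A reader could take that as reassurance about 26 weeks of drug unless it stood beside a comparison that carries the Week 13 events forward.

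**Working it through.** **The plan's own figure.** 100 evaluable per arm with 20% non-evaluable gives 100 / (1 − 0.20) = 125 per arm, as stated in Protocol 8.7. The documents give no expected decrease rate, margin or CI width, so there is no Week 26 precision to reproduce.

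**Time on blinded drug.** The window opens on Day 170 and data run to last blinded dose + 7 days: 170 − 7 = Day 163.

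**Formulas.** Per arm, let N be evaluable men, p the Week 13 decrease rate, r the IBD response rate and h the rate of new decreases in Part B.
- Men in the Week 26 figure: N(1 − p)r
- Observed-case proportion: h
- Any-time proportion over all N, counting men who leave as non-events afterwards: p + (1 − p)rh
- Product form, censoring men who leave: 1 − (1 − p)(1 − h)

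**Inputs.** N = 100 (Protocol 8.7; SAP 1.3 pools this target over two studies, so this trial's arms may be smaller). r = 59% v 41%, from the earlier Phase 2 Crohn's study in Protocol 1.3.2, for illustration only. p and h are assumed. The arithmetic treats all decreases as concentration decreases and assumes no Part B loss.

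**Worked line (15% v 5%, then 5% v 5%).** Men at Week 26: 100 × 0.85 × 0.59 = 50 v 100 × 0.95 × 0.41 = 39. Observed-case: 5% − 5% = 0.0. Any-time: 0.15 + 0.85 × 0.59 × 0.05 = 17.5% v 0.05 + 0.95 × 0.41 × 0.05 = 6.9%, a difference of +10.6. Product: (1 − 0.85 × 0.95) − (1 − 0.95 × 0.95) = 19.25% − 9.75% = +9.5.

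Differences are filgotinib minus placebo in points, with unstratified Wald 95% half-widths:

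| Assumed p, then h | Week 13 | Week 26 observed-case (n) | Any-time | Product |
|---|---|---|---|---|
| 5 v 5, then 5 v 5 | 0.0 | 0.0 ± 8.9 (56 v 39) | +0.9 ± 7.2 | 0.0 |
| 15 v 5, then 5 v 5 | +10.0 | 0.0 ± 9.1 (50 v 39) | +10.6 ± 9.0 | +9.5 |
| 20 v 5, then 5 v 5 | +15.0 | 0.0 ± 9.2 (47 v 39) | +15.4 ± 9.6 | +14.25 |
| 15 v 5, then 15 v 5 | +10.0 | +10.0 ± 12.0 (50 v 39) | +15.6 ± 9.6 | +18.0 |
| 5 v 5, then 20 v 5 | 0.0 | +15.0 ± 12.5 (56 v 39) | +9.3 ± 8.8 | +14.25 |

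**With measurement noise.** A simulation took the mean of two samples per visit, with lognormal error, single-sample CV of 30% to 60%, affected men falling to 30% of baseline, and IBD response of 60% v 45% unrelated to sperm risk. Differences in points are given from CV 30% to CV 60%:

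| Affected on filgotinib | Observed-case | Any-time | True cumulative if nobody left |
|---|---|---|---|
| None | 0.0 | +0.1 to +1.1 | 0.0 |
| 10% by Week 13 | +0.4 to +1.1 | +9.8 to +8.3 | +9.7 to +7.3 |
| 10% after Week 13 only | +9.5 to +7.2 | +5.8 to +5.0 | +9.4 to +6.4 |
| 10% by Week 13 and 10% after | +10.9 to +8.9 | +15.4 to +12.1 | +19.1 to +13.7 |

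The observed-case figure kept 49% to 59% of filgotinib men and 40% to 45% of placebo men. It is close to the truth for late harm, nearly blind to early harm, and about 5 to 8 points short for mixed harm.

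**The case against.** The strongest reply is that nothing is lost, and much of it stands. The primary analysis compares the arms at Week 13 with a CI. SAP 6.5.2 tabulates every threshold by arm at Week 13, and SAP 6.6.2 follows the Week 13 decreasers by arm for reversibility. A reader might infer that men harmed early disappear from the results. The documents do not support that.

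A reader might also infer that the any-time display is a bare count. SAP section 3 promises numbers and percentages for categorical variables, and SAP 3.1 puts the analysis set in each table's subtitle, so a percentage and a named set are probable. SAP 3.1.2 is not in the public text and may define the set. What remains missing in the visible text is an explicit by-arm denominator, a difference and a CI.

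Nor does the SAP depart from the protocol, which plans a descriptive summary at Week 26. A cumulative proportion is a different quantity, and men who stop at Week 13 have had only about one cycle of drug. It therefore belongs beside the endpoint and should not replace it.

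The product form can be worked out from planned figures, since p is reported by arm and h is essentially the observed-case proportion. A reader would still have to see the need for it, and would have no CI.

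The treatment-sequence displays in SAP 6.5.1 do not fill the gap. They carry an exact CI and, under the secondary-analysis rule ("data up to the last dose date of any study drug + 7 days"), keep men who switched from blinded to open-label filgotinib. They still omit the Week 13 decreasers who stopped drug and do not compare randomised arms.

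**Conclusion.** The concern holds in a limited form. The Week 26 observed-case proportion is conditional on IBD response, no Week 13 sperm decrease and continued blinded drug, and it is not labelled so. Under harm complete by Week 13 its expected difference is zero in the closed form and about +0.4 to +1.1 points with measurement noise, against any-time differences of roughly +8 to +15 points on the assumed inputs. No visible display gives a by-arm proportion through Week 26 with a difference and CI.

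The reach is modest. Early harm is measured at Week 13, late-only harm does show in the observed cases, and the endpoint is descriptive. All magnitudes rest on decrease rates, response rates and noise levels that the documents do not supply for this trial. The direction follows from the trial's flow and does not depend on them.

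**What to change.** In SAP 6.2:

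1. Label the Week 26 figure *conditional on no Week 13 sperm decrease and continued blinded treatment*, give n per arm, and point to the disposition table in SAP 4.1.
2. Keep the any-time count, including out-of-window decreases. Present it by randomised arm as n/N (%) over subjects evaluable at baseline and Week 13, using blinded-period data, with the Appendix 2 Mantel-Haenszel difference and 95% CI. A man whose only decrease was out of window and who has no evaluable Week 13 collection lies outside N, so show such men by arm beneath the table. Footnote that men who leave blinded drug count as non-events afterwards: late harm is understated, and unequal follow-up can shift the difference slightly (+0.1 to +1.1 points under no effect in the simulation).
3. Optionally add 1 − (1 − p)(1 − h) as a sensitivity figure, stating that it assumes leaving blinded drug is unrelated to later risk. If affected men respond at 40% rather than 60%, it is 1% to 4% too low for early harm, about 16% for mixed harm and 30% to 32% for late harm.

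The study has passed the second interim analysis time points, so mark the table as specified after unblinding.

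The cost is one label and one supportive table from data already collected. Precision is modest: at decrease rates of 8% to 16%, the any-time half-width is about 9 to 11 points with 100 evaluable per arm and 13 to 16 with 50. The product form is wider, at 13.0 to 14.6 and 19.0 to 21.0.

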Measure of intervention effect and handling of intercurrent events	Measure of treatment effect assuming that intercurrent event of early termination prior to Week 13 does not occur. Subjects who had missing data at Week 13 due to early termination will be assumed to be MAR and data will be imputed by conditional quantile estimation using the quantile regression model specified for the primary analysis using the methods of Bottai and Zhen.
Population level summary measure	Median Difference between treatment groups, comparing those assigned to filgotinib versus those assigned to placebo in the change and percentage change from baseline at Week 13 for a continuous outcome.
Estimators	Main estimator: Imputed datasets will be analyzed using quantile regression models used for primary analysis to obtain estimates and standard errors (standard errors obtained through bootstrap methods). Results of the estimates and standard errors will be combined using Rubin's rule to estimate the median difference (filgotinib – placebo) in change or percentage change from baseline, 95% CI for the sperm/semen parameter of interest.

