8.5. Statistical Analysis

8.5.1. Primary Analysis

The primary endpoint is the proportion of subjects with a $\geq 50\%$ decrease from baseline in sperm concentration at Week 13. A cumulative distribution plot for the percent change from baseline in sperm concentration at Week 13 for each treatment group will be constructed. The x-axis will display percent changes from baseline in sperm concentration ranging from 100% decrease (ie, -100 % or azoospermia) to the maximal observed increase. The y-axis will display the proportion of subjects who experienced a percentage change in sperm concentration equal to or less than the corresponding x-axis value at Week 13. This method is suggested in FDA’s Guidance for Industry (October 2018): “Testicular toxicity: Evaluation During Drug Development”. The proportion of subjects experiencing at least a 50% decrease in sperm concentration from baseline will be calculated for each treatment group. The difference between the filgotinib and placebo groups will be calculated together with the associated 95% confidence interval (CI).

Subjects who have 2 samples available at Week 13 will be included in the primary analysis. Sensitivity analyses will be performed to evaluate the impact of different missing data patterns on the primary analysis. Details of the sensitivity analyses will be provided in the SAP.

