1.3. Sample Size and Power

Results of this study will be pooled with the results of a separate study being conducted in subjects with rheumatic diseases (GLPG0634-CL-227 [MANTA-RAY]) with the same objectives. The total planned number of subjects in both studies combined will be up to approximately 250 subjects.

A sample size of approximately 100 evaluable subjects per group (ie, 100 subjects in the filgotinib 200 mg group and 100 subjects in the placebo group) is adequate for the purposes of estimating cumulative distribution curves and producing a 95% confidence interval (CI) width that is reasonably narrow for the proportion of subjects in each group who experience a $\geq 50\%$ decrease in sperm concentration compared to baseline. An evaluable subject is defined as a subject with 2 semen samples at both baseline and at Week 13 that are eligible for mean calculation for sperm concentration, with visit window assignment for the mean calculation based on the date of the first of 2 evaluable sample collections. This 200 subject sample size is suggested in FDA's guidance on testicular toxicity studies {[U. S. Department of Health and Human Services \(DHHS\) 2018](#)}. Assuming a 20% rate of non-evaluable subjects at Week 13, up to 250 subjects may be enrolled to obtain 200 evaluable subjects.

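### The supportive Week 13 analysis of the continuous semen endpoints is expected to reproduce the completer estimate, so agreement with the primary analysis says little about early termination

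*SAP*

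**What the plan says.** - **Primary analysis (SAP 6.2).** The continuous endpoints are analysed as observed cases, in men with two evaluable samples at baseline and two at Week 13. The median difference comes from a quantile regression. Its covariates are the baseline value and, for parameters other than concentration, a two-level concentration stratum. Treatment is implied by the contrast. No post-baseline measurement enters.
- **Supportive analysis (SAP 6.4).** A hypothetical-strategy estimand is offered in support of the primary analysis: "Measure of treatment effect assuming that intercurrent event of early termination prior to Week 13 does not occur". Men without a Week 13 value because they stopped early are treated as missing at random (MAR). For them, "data will be imputed by conditional quantile estimation using the quantile regression model specified for the primary analysis". In the next step, "Imputed datasets will be analyzed using quantile regression models used for primary analysis to obtain estimates and standard errors", with bootstrap standard errors and Rubin's rule.
- **Protocol 8.5.1**, on the primary (binary) endpoint: "Sensitivity analyses will be performed to evaluate the impact of different missing data patterns on the primary analysis", with the details left to the SAP.
- **SAP 1.3**: "Assuming a 20% rate of non-evaluable subjects at Week 13", the enrolment ceiling is 250 men for 200 evaluable.

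The available rows of SAP 6.4 for the continuous endpoints describe no auxiliary variable, delta adjustment, reference-based imputation or tipping-point analysis.

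**The concern.** The imputation model and the analysis model are the same model with the same covariates, and only the outcome is missing. The imputed men therefore bring nothing that the completers did not already supply. If the supportive result is then set beside the primary one and the two agree, a reader will naturally take this as evidence that early termination does not matter. Near-agreement was to be expected whatever happened to the men who stopped.

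In a testicular-safety trial, the departure of most interest is that men who stopped filgotinib early had larger falls than those who stayed. An analysis built this way cannot detect that.

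**Working it through.** **1. The plan's own figure.** 200 / (1 − 0.20) = 250 men, or 100 / 0.80 = 125 per arm. This reproduces SAP 1.3. At 20%, 125 × 0.20 = 25 men per arm would be non-evaluable from all causes. Only those missing through early termination are imputed, so on planning terms 25 is an upper bound.

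**2. Why the estimates coincide in expectation.** The completer median fit b solves

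Σ x(0.5 − 1[y < x′b]) = 0.

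An imputed value is a fitted conditional quantile at a uniformly random level. It falls below x′b with probability 0.5 at every x, so each imputed man adds an expected score of x(0.5 − 0.5) = 0. Hence b still solves the combined equation in expectation. The argument does not need the model to be correctly specified.

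**3. Simulation.** There were 150 trials of 125 men per arm, with about 20% missing and 20 imputations. Each imputation fitted quantiles to a bootstrap resample of completers. Median regression was then refitted and combined by Rubin's rule. The following are assumptions, not taken from the documents:
- log-normal baseline concentration (median 65 M/mL, log SD 0.6, floor 15);
- log-scale SD of change 0.45;
- the shifts applied to filgotinib stoppers;
- this reading of conditional quantile imputation.

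Mean median difference, filgotinib − placebo, in percentage points:

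| True shift in filgotinib stoppers | Completers | Imputed | Full data |
|---|---|---|---|
| 0 | −0.52 | −0.41 | 0.62 |
| −40 | −0.52 | −0.41 | −5.88 |
| −60 | −0.52 | −0.41 | −7.80 |
| −40, misspecified model, missingness dependent on baseline | 8.54 | 8.41 | 2.80 |

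The first three rows share the same observed data, so their first two columns must be identical. That is the point: the shift lies wholly in values the analysis never sees.

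The more informative result is the gap between imputed and completer estimates in those rows:
- mean −0.41 − (−0.52) = 0.11, SD 1.53, largest 4.96;
- relative to the completer SE of 8.33, the SD is 1.53 / 8.33 = 0.18;
- correlation 0.984 (0.980 in the fourth row);
- SE 8.33 for completers and 8.62 for imputed.

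**4. A second, separately built simulation.** This used 120 trials and a 40% relative fall in filgotinib stoppers. It gave −0.55 for completers, −0.54 imputed and −8.82 for full data. The correlation was 0.98, and the mean absolute gap was about 1.1 against a sampling SD of about 7.5.

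**5. Would a delta adjustment respond?** Subtracting 40 points from the imputed filgotinib values (no floor applied) moved the mean estimate from −0.41 to −6.92, a change of −6.51.

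**The case against.** Several objections stand and limit the point.

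- **The estimand is hypothetical by design.** It assumes early termination away and declares MAR openly, so its silence on the effect of stopping is not an error. What remains is that it does not test MAR and so gives little support.
- **The identity is in expectation.** A single run carries imputation noise, up to 4.96 points in these trials. The interval method also differs: rank-based in SAP 6.2, bootstrap with Rubin's rule in SAP 6.4. To say that the two analyses can never differ would be too strong.
- **A reader might infer that the commitment in Protocol 8.5.1 is unmet.** The documents do not support that. The sentence concerns the binary primary endpoint, and the part of SAP 6.4 that sets out its supportive estimand is not in the reviewed text. SAP 3.7.3 also refers to a sensitivity analysis admitting men with a single evaluable sample, although that does not help men with none.
- **A reader might infer that harm in early stoppers would go unseen.** That is also too strong. SAP 6.2 displays decreases of at least 50% in sperm concentration at any time up to Week 26, including those outside visit windows. Protocol 8.3 commits to summarising missingness by arm, stratum and baseline demographics. Neither enters this model or yields an adjusted median difference, but both could show a signal.
- **The size is driven by assumptions.** The 20% covers all causes, and a shift in one arm only has no basis in the documents.

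MAR without a departure analysis is a common choice. That lowers the urgency but does not answer the algebra.

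**Conclusion.** The point holds for the continuous semen endpoints. The supportive analysis in SAP 6.4 is a valid MAR estimate of the hypothetical estimand, but it is centred on the completer estimate. Under the stated assumptions the gap averaged 0.11 points with an SD of 1.53, under a fifth of the standard error, and the standard error itself barely changed. Agreement with the primary analysis should not be read as robustness to early termination.

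The near-identity rests on the shared model and does not depend on the assumed shifts. The possible size of the missed effect does: full-data differences of about −6 to −9 points arose only under large assumed falls in filgotinib stoppers and 20% missing, and fewer early terminators would mean a smaller effect. The documents do not give the number of early terminators. No conclusion is drawn about the binary endpoint.

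**What to change.** In SAP 6.4:

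1. State that the MAR result for the continuous endpoints is expected to reproduce the completer estimate, and is not evidence about departures from MAR.
2. Add a delta-adjusted analysis on the same imputed datasets. Shift the imputed percent change in sperm concentration of filgotinib early terminators down in fixed steps, for example 0, −10, −20, −30, −40 and −50 points, floored at −100%. Use the matching shift for absolute change (step / 100 × baseline value) and for the other parameters.
3. Report the median difference and 95% CI at each step, with the number of men imputed per arm.
4. Report the smallest shift at which the 95% CI excludes zero in the direction of harm. The plan sets no margin or decision rule, so this should be labelled a descriptive sensitivity result.

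The cost is one more supportive analysis, with no new data and no new imputation. The stated robustness may look less favourable. The SAP Introduction provides for changes after finalisation to be documented in the clinical study report; if added after unblinding, the series should be marked post hoc.
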